6.3 Measures to Minimize/Avoid Bias

Treatment will be double-blind. Neither the investigator nor the subject will have knowledge of the treatment assignment.

Treatment assignments will be based on a computer-generated randomization code provided by the OPDC Biostatistics Department. Sponsor personnel, including those

involved in monitoring, data management, and data analysis, will not have access to the treatment code during the trial. The bioanalytical laboratory will also be sent the randomization code. Access to the treatment codes will be restricted to personnel charged with generating and maintaining randomization files, packaging trial medication, and reporting serious adverse events (SAEs) to regulatory agencies. The randomization will be stratified by trial site and designed to allocate subjects in a 1:1:1 ratio to high dose centanafadine, low dose centanafadine, or placebo (see Section 6.1).

Procedures for breaking the blind can be found in Section 8.8.8.

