9.4.1.6 Other Efficacy Endpoint Analysis

Not applicable.

9.4.2 **Safety Analysis**

9.4.2.1 **Adverse Events**

All AEs will be coded by system organ class and MedDRA preferred term. The incidence of the following events will be summarized by treatment group:

- **TEAEs**
- TEAEs by severity
- TEAEs potentially causally related to the IMP
- TEAEs with an outcome of death
- Serious TEAEs
- TEAEs leading to discontinuation of the IMP

9.4.2.2 **Clinical Laboratory Data**

Summary statistics for changes from baseline in the routine clinical laboratory measurements will be provided. In addition, potentially clinically significant laboratory

results will be identified using criteria prospectively defined in the SAP and will be summarized. Change from baseline in fasting triglycerides and total cholesterol at Week 8/ET will be analyzed using analysis of covariance including treatment group, trial center as fixed factors and baseline as covariate.

9.4.2.3 **Physical Examination and Vital Signs Data**

By-subject listings will be provided for physical examination findings. Summary statistics for changes from baseline in vital signs will be provided. Potentially clinically significant results in vital signs and body weight will also be summarized. In addition, change from baseline in body weight and percentage of change from baseline in body weight will be analyzed using MMRM.

9.4.2.4 **Electrocardiogram Data**

Summary statistics for change from baseline and incidence of clinically significant changes will be calculated for ECG parameters.

For the analysis of OT and OTc, data from 3 consecutive complexes (representing 3 consecutive heart beats) will be measured to determine average values. The following QT corrections will be used for reporting purposes in the clinical study report:

- QTcF is the length of the QT interval corrected for heart rate by the Fredericia formula: $OTcF = OT / (RR)^{0.33}$
- QTcN is the length of the QT interval corrected for heart rate by the FDA Neuropharm Division formula: $QTcN = QT / (RR)^{0.37}$

In addition, potentially clinically significant ECG results will be identified using criteria prospectively defined in the SAP and will be summarized.

9.4.2.5 **Other Safety Data**

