3.3 Trial Population

Subjects are 18 to 65 years of age (inclusive), with a primary diagnosis of BED of at least moderate severity, with a history of at least 2 binge eating days per week for 6 months prior to screening and at least 3 binge eating days in each week during the previous 14 days of a subject's screening period according to the subject's binge diary as reviewed at baseline, a rating of 4 or higher on the Clinical Global Impression - Severity (CGI-S) at screening and baseline, and a body mass index (BMI) of 18 to 45 kg/m², inclusive. Subjects with a lifetime history or current diagnosis of bulimia nervosa or anorexia nervosa are excluded.

Approximately 228 adult subjects with BED are anticipated to be screened with the expectation that approximately 126 eligible subjects are to be randomized (42 subjects per treatment arm). The randomization is stratified by trial site.

4 Sample Size

Assuming a treatment difference of 1.1 points with a standard deviation of 1.7 in the mean change from baseline in binge eating days per week at Weeks 7-8 in either centanafadine dose group (high dose centanafadine or low dose centanafadine) compared to the placebo group (effect size = 0.65), a sample size of 114 evaluable subjects (38 in each treatment arm) yield at least 80% power to detect the treatment effects at a 2-tailed significance level of 0.05. Approximately 126 subjects are randomized to ensure 114 evaluable subjects in the study. The power and sample size were obtained using the PASS 14 (2015) statistical computing software.

5 Statistical Analysis Datasets

The following datasets are defined for this trial:

- Randomized Analysis Set comprises all subjects who are randomized in the double-blind treatment period. Subjects are considered randomized subjects when they are assigned a treatment group at the baseline visit.
- Safety Analysis Set comprises those randomized subjects in the double-blind treatment period who receive at least 1 dose of double-blind IMP. Subjects will only be excluded from this population if there is documented evidence (ie, numbers of drug dispensed are equal to numbers of drug returned, or no IMP dispensed at all) that the subject did not take IMP. If a subject is dispensed IMP and is lost to follow-up, he/she is considered as exposure to IMP.

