9.4 Clinical Laboratory Data

Clinical laboratory tests include serum chemistry, hematology, and urinalyses analyses. Potentially clinically relevant laboratory test abnormalities will be listed by subject and by test. Criteria for potentially clinically relevant laboratory test abnormalities are provided in Appendix 2. Subjects with aspartate aminotransferase (AST) or alanine aminotransferase (ALT) \geq 3 × upper limit of normal value and total bilirubin \geq 2 × upper limit of normal value or baseline will be listed.

The incidences of potentially clinically relevant laboratory tests abnormalities based on observations during scheduled and unscheduled post-baseline visits will be tabulated by treatment group. Summary statistics for clinical laboratory measurements and changes from baseline will be presented by treatment group and scheduled visit. Change from baseline in fasting triglycerides and total cholesterol at Week 8/ET will be analyzed using ANCOVA including treatment group as fixed factor and baseline as covariate.

If laboratory tests assessments are repeated for the same mapped trial visit, the last repeated values will be used for summary tables. This is accomplished by sorting subject data by visit date and visit time (if applicable) within the same trial visit. If the lab data are recorded as ranges (ie, including < or > limit of quantification), these data are not

included in the calculations for changes from baseline but included in the calculations for incidences.

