9.5 Physical Examination Data

By-subject listings will be provided for physical examination findings.

Body weight and BMI collected at scheduled visits will be mapped to the weeks per specification in Table 5.2-2. Potentially clinically relevant changes in body weight will be summarized by treatment group and/or by week.

In addition, change from baseline in body weight and percentage of change from baseline in body weight will be analyzed similarly using MMRM model including treatment group, trial center, visit week, and an interaction term of treatment by visit week as fixed effect terms, and interaction term of baseline weight by week as covariates. Change from baseline in body weight percentage of change from baseline in body weight at all mapped visits and last visit will also be explored using ANCOVA model, including treatment and trial center as fixed factors and baseline weight as covariate.

Change from baseline in BMI will be summarized by treatment group and week. In addition, frequencies and percentage of subjects will be provided for classification of BMI by treatment group and week. Shift table will be provided as needed.

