10.11 Columbia-Suicide Severity Rating Scale (C-SSRS)

Suicidality will be monitored during the trial using the C-SSRS. The C-SSRS is a semistructured interview that captures the occurrence, severity, and frequency of suiciderelated thoughts and behaviors during the assessment period. The interview includes definitions and suggested questions to solicit the type of information needed to determine if a suicide-related thought or behavior has occurred.

The C-SSRS has a "Screening/Baseline" version, which will be completed at screening and a "Since Last Visit" version that will be completed at all scheduled visits (including the ET visit, if applicable). There are a maximum of 19 items to be completed: 7

required, 10 potential additional items if there is a positive response to a required item, and 2 items for suicide/suicide behavior present during the interview. The C-SSRS uses dichotomous scales (i.e., yes or no), Likert scales, and text or narrative to further describe the thoughts or behaviors.

11 Pharmacokinetic Analyses

Sparse PK samples will be evaluated to confirm compliance with dosing. Concentrations will be listed in the bioanalytical report.

12 Pharmacodynamic Analyses

No pharmacogenomic analyses is planned.

13 Pharmacogenomic Analyses

No pharmacogenomic analyses is planned.

14 Interim Analysis

No interim analyses is planned.

15 Changes in the Planned Analyses

Trial center will not be included in ANCOVA model for analyses of change from baseline in fasting triglycerides and total cholesterol at Week 8/ET.

16 References

- 3. Little RJA. Pattern-mixture models for multivariate incomplete data. J Am Stat Assoc. 1993; 88:125-34.
- 4. Little RJA. Modeling the drop-out mechanism in repeated measures studies. J Am Stat Assoc. 1995; 90:1112-21.

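### The SAP drops trial center from the triglyceride and total cholesterol ANCOVA without a reason; the treatment difference stays unbiased, but reported standard errors are slightly conservative if lipid change differs between sites

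*SAP*

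**What the plan says.** Protocol 9.4.2.2 (Clinical Laboratory Data) specifies the lipid analysis with center in the model: "Change from baseline in fasting triglycerides and total cholesterol at Week 8/ET will be analyzed using analysis of covariance including treatment group, trial center", with baseline as covariate.

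SAP 9.4 (Clinical Laboratory Data) specifies the same endpoints with a smaller model: "ANCOVA including treatment group as fixed factor and baseline as covariate". SAP Section 15 declares the difference: "Trial center will not be included in ANCOVA model for analyses of change from baseline in fasting triglycerides and total cholesterol at Week 8/ET". Neither place explains it.

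Both documents make site the stratification factor. Protocol 6.3: "The randomization will be stratified by trial site and designed to allocate subjects in a 1:1:1 ratio". SAP 3.3: "The randomization is stratified by trial site".

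Elsewhere the SAP keeps center:
- the primary MMRM (8.2.1) and the key secondary MMRM (8.3);
- the CMH tests and the EDE-Q7 ANCOVA (8.5);
- the exploratory efficacy ANCOVAs (8.6);
- body weight (9.5), which is "analyzed similarly using MMRM model including treatment group, trial center, visit week, and an interaction term of treatment by visit week", together with a body-weight ANCOVA that also includes center.

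**The concern.** When allocation is balanced within sites, site effects largely cancel from the treatment contrast. A model without site still counts them as residual noise. Its standard error then describes a less precise experiment than the one that was run, and a real lipid change in either direction is somewhat harder to see. Change in total cholesterol and triglycerides is named among the safety endpoints in Protocol Section 3, so this is not incidental output.

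The treatment of lipids is also out of line with the rest of the SAP. Body weight is the closest comparison: it is a safety variable, and Appendix 4 lists its tables on the Safety Analysis Set, as it does the lipid ANCOVA table. Center is considered workable there, and a rule for pooling small centers exists in SAP 8.2.3.2. Sparse centers therefore do not obviously explain the exception.

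**Working it through.** **What the documents supply.** They give no planned precision for the lipid ANCOVA. The only design calculation is for the primary endpoint (difference 1.1, SD 1.7, two-sided 0.05, 80% power; Protocol 9.1). It reproduces: n per arm = 2 × (1.960 + 0.842)² × (1.7/1.1)² = 2 × 7.85 × 2.388 = 37.5, rounded up to 38, or 114 in total. With 126 randomized, the implied loss is 12/126 = 9.5%. The lipid model does not affect this calculation, which is used here only for the numbers of subjects.

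**Assumptions, not in the documents.** Number of sites: 10 to 30. Block size: 3, with 6 as a check. Share of residual variance lying between sites after baseline adjustment (ICC): 0 to 0.20.

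**Analytic check.** Let σ² be the residual variance including site, with n subjects per arm. Under full within-site balance:
- true variance of the treatment difference ≈ (2/n) × σ² × (1 − ICC);
- variance reported without center ≈ (2/n) × σ²;
- ratio of reported to true SE = 1/√(1 − ICC).

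This gives 1.010 at ICC 0.02, 1.026 at 0.05, 1.054 at 0.10 and 1.118 at 0.20.

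**Simulation A.** Three arms, 126 subjects, permuted blocks of 3 within unequal sites, pooling of the SAP type, 3000 runs per setting. The table shows mean 95% interval width without center divided by width with center, and coverage across the three site numbers.

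| ICC | 10 sites | 20 sites | 30 sites | Coverage without center | Coverage with center |
|---|---|---|---|---|---|
| 0 | 0.997 | 0.991 | 0.986 | 94.8-95.5% | 94.8-95.4% |
| 0.02 | 1.005 | 0.999 | 0.995 | 94.5-95.3% | 94.4-95.5% |
| 0.05 | 1.019 | 1.014 | 1.008 | 95.3-96.3% | 94.8-95.7% |
| 0.10 | 1.042 | 1.039 | 1.032 | 95.8-95.9% | 94.8-95.1% |
| 0.20 | 1.099 | 1.095 | 1.088 | 96.9-97.1% | 94.9-95.1% |

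Blocks of 6 gave similar ratios (for example 1.017 at 10 sites and ICC 0.05). The actual spread of the treatment estimates is nearly the same under both models: 0.210 without center against 0.211 with it at 10 sites and ICC 0.10. The estimate is therefore hardly affected; what changes is the reported uncertainty.

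**Simulation B.** 114 subjects, mean model SE without center against with center:
- ICC 0.05: 0.2284/0.2239 = 1.020 (10 sites); 0.2289/0.2261 = 1.012 (20 sites).
- ICC 0.10: 0.2272/0.2171 = 1.047 (10 sites); 0.2281/0.2195 = 1.039 (20 sites).
- ICC 0: fitting center costs 0.2297/0.2292 = 1.002 (10 sites) to 0.2322/0.2291 = 1.014 (20 sites).

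At 10 sites and ICC 0.10 the SE without center is 0.2272 against an empirical SD of 0.219, about 4% too large.

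**The case against.** The change is openly declared in Section 15 and carried through consistently in SAP 9.4, so no analyst could run the wrong model. A reader might infer a hidden conflict between protocol and SAP. The documents do not support that: the SAP supersedes the protocol here in the place meant for such changes. What is missing is the reason.

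A reader might also infer that the lipid comparison is invalid, or that its intervals are necessarily too wide. Neither follows. The error is conservative, and it exists only if lipid change differs between sites, which nothing in the documents shows. Baseline is already a covariate, so stable site differences in lipid level are largely removed and only differences in change remain. The SAP does not mention intervals for this model; they are assumed as standard output. The analysis lies outside the fixed testing sequence (SAP 8.4), and lipids are also summarized descriptively and by threshold (SAP 9.4, Appendix 2).

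It is tempting to argue that sites must differ because Protocol 8.7.1 asks for fasting only where possible. That is speculative. The Schedule of Assessments lists the baseline, Week 4 and Week 8/ET laboratory draws as fasting, and both analysis statements are confined to fasting lipids. If non-fasting samples did enter, center would be only a crude proxy for fasting status.

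One practical objection stands in full: SAP 8.2.3.2 defines small centers by the primary efficacy endpoint, so those pooled centers need not contain lipid data in every arm. The rule has to be restated for this analysis.

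The rest of the objection limits the importance of the point. It supplies no reason for leaving the stratification factor out of this analysis while keeping it for body weight.

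**Conclusion.** The point holds as a minor one. The SAP removes the stratification factor from the lipid ANCOVA without a reason, against the protocol and against its own practice in the other models. There is no bias in the treatment difference and no inflation of type I error. If lipid change differs between sites, the reported standard errors are conservative: about 1-2% larger than with center at an ICC of 0.05, about 3-5% larger at 0.10, and roughly 9-10% in interval width only at 0.20. At 0.02 or below there is essentially nothing to gain. These sizes rest on an assumed number of sites, block size and ICC; the direction does not. The sample size and the confirmatory tests are unaffected.

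**What to change.** In SAP 9.4, restore trial center as a fixed factor in the triglyceride and total cholesterol ANCOVA, in line with Protocol 9.4.2.2. State that small centers are pooled by the SAP 8.2.3.2 algorithm applied to subjects evaluable for the lipid endpoint. Delete the Section 15 entry, and keep the model without center as a sensitivity check.

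The cost is one model term, a sentence on pooling and the removal of one entry. The statistical downside is a standard error up to about 1.4% wider if sites do not differ.

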Appendix 1 Criteria for Identifying Vital Signs and Weight of Potential Clinical Relevance

Variable	Criterion Value ^a	Change Relative to Baseline ^a
Heart Rate ^b	> 100 bpm < 50 bpm	≥ 10 bpm increase ≥ 10 bpm decrease
Systolic Blood Pressure ^b	≥ 140 mmHg < 90 mmHg	≥ 20 mmHg increase ≥ 20 mmHg decrease
Diastolic Blood Pressure ^b	≥ 90 mmHg < 60 mmHg	≥ 10 mmHg increase ≥ 10 mmHg decrease
Orthostatic Hypotension	≥ 30 mmHg decrease in systolic blood pressure or a ≥ 20 mmHg in diastolic blood pressure after at least 3 minutes of standing compared to the previous supine blood pressure.	Not Applicable (baseline status not considered)
Orthostatic Tachycardia	≥ 25 bpm increase in heart rate from supine to standing	Not Applicable (baseline status not considered)
Weight	-	≥ 7% increase ≥ 7% decrease

a In order to be identified as potentially clinically relevant, an on-treatment value must meet the "Criterion Value" and also represent a change from the subject's baseline value of at least the magnitude shown in the "Change Relative to Baseline" column.

b As defined in "Supplementary Suggestions for Preparing an Integrated Summary of Safety Information in an Original NDA Submission and for Organizing Information in Periodic Safety Updates," FDA Division of Neuropharmacological Drug Products draft (2/27/87).

Appendix 2 Criteria for Identifying Laboratory Values of Potential Clinical Relevance

Laboratory Tests Criteria			
Chemistry			
AST (SGOT) $\geq 3 \times \text{upper limit of normal (ULN)}$			
ALT (SGPT)	$\geq 3 \times ULN$		
Alkaline phosphatase	$\geq 3 \times ULN$		
BUN	\geq 30 mg/dL		
Creatinine	$\geq 2.0 \text{ mg/dL}$		
Uric Acid			
Men	$\geq 10.5 \text{ mg/dL}$		
Women	$\geq 8.5 \text{ mg/dL}$		
Bilirubin (total)	$\geq 2.0 \text{ mg/dL}$		
Creatine Phosphokinase (CPK)	> 3 x ULN		
Hematology			
Hematocrit			
Male	\leq 37 % and decrease of \geq 3 percentage points from Baseline		
Female	\leq 32 % and decrease of \geq 3 percentage points from Baseline		
Hemoglobin			
Men	$\leq 11.5 \text{ g/dL}$		
Women	$\leq 9.5 \text{ g/dL}$		
White blood count	$\leq 2,800/ \text{ mm}^3 \text{ or } \geq 16,000/ \text{ mm}^3$		
Eosinophils	≥ 10%		
Neutrophils	≤ 15%		
Absolute neutrophil count	\leq 1,500/ mm ³		
Platelet count	\leq 75,000/ mm ³ or \geq 700,000/ mm ³		
Urinalysis			
Protein	Increase of ≥ 2 units		
Glucose	Increase of ≥ 2 units		
Additional Criteria			
Chloride	\leq 90 mEq/L or \geq 118 mEq/L		
Potassium	$\leq 2.5 \text{ mEq/L or} \geq 6.5 \text{ mEq/L}$		
Sodium	$\leq 126 \text{ mEq/L or} \geq 156 \text{ mEq/L}$		
Calcium	$\leq 8.2 \text{ mg/dL or} \geq 12 \text{ mg/dL}$		
Glucose			
Fasting	$\geq 100 \text{ mg/dL}$		
Non-Fasting	$\geq 200 \text{ mg/dL}$		
Total Cholesterol, Fasting	$\geq 240 \text{ mg/dL}$		
LDL Cholesterol, Fasting	$\geq 160 \text{ mg/dL}$		
HDL Cholesterol, Fasting			
Male	< 40 mg/dL		
Female	< 50 mg/dL		
Triglycerides, Fasting	≥ 150 mg/dL		

Appendix 3 Criteria for Identifying ECG Measurements of Potential Clinical Relevance

Variable	Criterion Value ^a	Change Relative to Baseline ^a
Rate		
Tachycardia	≥ 120 bpm	increase of ≥ 15 bpm
Bradycardia	≤ 50 bpm	decrease of ≥ 15 bpm
Rhythm		
Sinus tachycardia ^b	≥ 120 bpm	increase of ≥ 15 bpm
Sinus bradycardia ^c	≤ 50 bpm	decrease of ≥ 15 bpm
Supraventricular premature beat	all	not present → present
Ventricular premature beat	all	not present → present
Supraventricular tachycardia	all	not present \rightarrow present
Ventricular tachycardia	all	not present \rightarrow present
Atrial fibrillation	all	not present \rightarrow present
Atrial flutter	all	not present \rightarrow present
Conduction		
1° atrioventricular block	$PR \ge 200 \text{ msec}$	increase of ≥ 50 msec
2° atrioventricular block	all	not present \rightarrow present
3° atrioventricular block	all	not present \rightarrow present
Left bundle-branch block	all	not present \rightarrow present
Right bundle-branch block	all	not present \rightarrow present
Pre-excitation syndrome	all	not present \rightarrow present
Other intraventricular conduction block ^d	QRS \geq 120 msec	increase of ≥ 20 msec
Infarction		
Acute or subacute	all	not present \rightarrow present
Old	all	not present \rightarrow present
~~~		≥ 12 weeks post study entry
ST/T Morphological		_
Myocardial Ischemia	all	not present → present
Symmetrical T-wave inversion	all	not present $\rightarrow$ present
Increase in QTc	QTcF > 450  msec	
	(male) QTcF > 470 msec	
	(female)	

^a In order to be identified as potentially clinically relevant, an on-treatment value must meet the "Criterion Value" and also represent a change from the subject's baseline value of at least the magnitude shown in the "Change Relative to Baseline" column.

^b No current diagnosis of supraventricular tachycardia, ventricular tachycardia, atrial fibrillation, atrial flutter, or other rhythm abnormality.

^c No current diagnosis of atrial fibrillation, atrial flutter, or other rhythm abnormality.

[figure not shown]
^d No current diagnosis of left bundle branch block or right bundle branch block.

